4.2 Discussion of Study Design

Choice of Study Population

The inclusion and exclusion criteria are meant to identify a population of pediatric subjects that is well characterized as having FC as defined by Rome IV criteria.

Appropriateness of Measurements

Standard statistical, clinical, and laboratory procedures will be utilized in this study. All efficacy and safety-related measurements in this study are standard for assessing disease activity in subjects with FC. All clinical and laboratory procedures in this study are standard and generally accepted.

Suitability of Subject Population

Despite the fact that children with FC are commonly prescribed various and miscellaneous pharmacologic agents, it is notable that there are no approved products indicated for FC in children less than 6 years of age or well controlled trials of these frequently prescribed agents. Thus, effective treatments are needed to provide symptomatic relief in children less than 6 years of age with FC, with the evidence for safety and efficacy of these based on the results of adequate and well-controlled studies.

This study is being conducted in pediatric subjects aged 6 months to less than 2 years who meet Rome IV criteria for FC based on the linaclotide pediatric developmental program and discussions with regulatory agencies. Section 5.1 outlines the eligibility criteria and the eligible subject population.

Dose Justification

The dose selection in this study is based on extrapolation of efficacy and safety data from Phase 2 studies in FC subjects 2 to 17 years of age, Phase 3 studies in adult subjects with CIC, and a clinical research GC-C ontogeny study in pediatric patients.

In the Phase 2 FC study, Lin-MD-67, children (2- to 5-year-olds), were administered linaclotide doses of 18, 36, and 72 µg for 4 weeks. Those doses correspond to 1.8, 3.6, and 7.2 µg/kg in a 10 kg (22 pound) subject (minimum weight of a 2-year-old), respectively. Overall linaclotide was well tolerated across all doses evaluated in LIN-MD-67, the safety profile being consistent with that of the prior FC study LIN-MD-62 in 6 to 17 year-olds and prior studies in adults with CIC. There were no deaths, SAEs, AESIs (i.e., significant volume depletion and/or significant electrolyte abnormalities and/or ECG abnormalities that were considered by the investigator or sponsor to be related to diarrhea), or AEs leading to study drug discontinuation for LIN-MD-67 with all TEAEs experienced by subjects being mild or moderate in severity.

Additionally, in the GC-C ontogeny study MCP-103-311, GC-C mRNA expression in the small bowel was shown to be flat with no age-dependent trend in patients 6 months to < 18 years of age.⁶ The doses of 9, 18, and 36 µg QD being employed in Study M21-862 correspond to 1.8, 3.6 and 7.2 µg/kg in a 5 kg (11 pound) subject (minimum weight of a 6 month old), respectively and are therefore equivalent to the doses tested and safe in 2- to 5- year-old subjects on µg/kg basis and are expected to have an acceptable safety profile. Dose escalation between cohorts will be assessed based on the review of all available safety/tolerability data by an internal Dose Escalation Committee. Regarding risks, patients are closely monitored for AEs including diarrhea and well-defined AESIs. Safety measures are in place including stopping criteria, a safety monitoring plan, and an independent DSMB.

5 STUDY ACTIVITIES

5.1 Eligibility Criteria

Subjects must meet all of the following criteria in order to be included in the study. Anything other than a positive response to the questions below will result in exclusion from study participation.

Consent

- ✓ 1. The Subjects' LAR/parent/guardian must voluntarily sign and date an informed consent, approved by an independent ethics committee (IEC)/institutional review board (IRB), prior to the initiation of any screening or study-specific procedures.
- ✓ 2. The LAR/parent/guardian who will be completing the electronic diary (eDiary) is able to read and understand the assessments in the eDiary device and must undergo training
- ✓ 3. Subject's LAR/parent/guardian are willing and able to comply with procedures required in this protocol and do not have any neurodevelopmental disabilities that could impact their ability to complete the eDiary and study questionnaires.

Demographic and Laboratory Assessments

- ✓ 4. **Individuals** must be 6 months to less than 1 year and 11 months old, at the time the LAR/parent/guardian signs the informed consent in alignment with local requirements.
- ✓ 5. Subject has no condition or clinically significant findings on a physical examination, vital sign assessment, ECG, or clinical laboratory tests at Screening (Visit 1), as determined by the investigator, based on consideration of whether the finding could represent a safety concern or a condition that would be exclusionary, could prevent the subject from performing any protocol assessments, or could confound study assessments
- ✓ 6. Subject has weight-for-height/length ratio of \geq 3rd percentile for age 6 months to less than 24 months at the time the LAR/parent/guardian has provided signed consent. (Investigators can choose to use CDC or WHO growth charts based on their current clinical practice).
- ✓ 7. Laboratory values meet the following criteria within the screening of assessments period and prior to the first dose of study drug:
 - Serum alanine transaminase (ALT) $< 2 \times$ upper limit of normal (ULN);

Per investigator's discretion all other laboratory values obtained in the screening period prior to the first dose of study drug must not be considered clinically significant abnormalities.

- ✓ 8. Subject's LAR/parent/guardian must have not been directly or indirectly involved in the conduct and administration of this study as an investigator, study coordinator, or other study staff member. In addition, any subject, LAR/parent/guardian must not have a first-degree family member, significant other, or relative residing with him/her who are directly or indirectly involved in this study.

Disease/Condition Activity

- ✓ 9. Subject meets Rome IV criteria for FC as outlined below:
For at least 1 month before Screening (Visit 1), the subject must meet 2 or more of the following (a-e):
 - a) 2 or fewer defecations per week (with each defecation occurring in the absence of any laxative, suppository, or enema use during the preceding 24 hours)
 - b) History of excessive stool retention
 - c) History of painful or hard bowel movements (BMs)
 - d) History of large-diameter stools
 - e) Presence of a large fecal mass in the rectumAccompanying symptoms may include irritability, decreased appetite, and/or early satiety. The accompanying symptoms disappear immediately following passage of a large stool.
- ✓ 10. LAR/Parent/Guardian is willing to discontinue any laxatives used before the Preintervention Visit in favor of the protocol-permitted rescue medicine.
- 11. Based on the eDiary, the LAR/Parent/Guardian/Caregiver reports the subject did not have more than 1 loose, mushy stool (eDiary recorded stool consistency of 6 on the Bristol Stool Form Scale) or any watery stool (eDiary recorded stool consistency of 7 on the Bristol Stool Form Scale) with any SBM that occurred in the absence of laxative use on the calendar day of the BM **or** the calendar day before the BM during the 14 days before and up to enrollment/randomization (including the daily eDiary assessment reported before administration of the first dose of study intervention on the enrollment/randomization day).
- ✓ 12. Based on the eDiary, the Subject has an average of \leq 2 spontaneous bowel movements (SBMs) per week during the 14 days before the enrollment/randomization day and up to the enrollment/randomization (including the morning eDiary assessments reported before administration of first dose of study intervention on the enrollment/randomization day). An SBM is defined as a bowel movement (BM) that occurs in the absence of laxative, enema, or suppository use on the calendar day of the BM or the calendar day before the BM.
- ✓ 13. LAR/Parent/Guardian/Caregivers are compliant with eDiary requirements by completing daily assessments for 10 out of the 14 days immediately preceding the enrollment/randomization visit.

Subject History

- ✓ 14. No conditions that could **interfere with drug absorption** including but not limited to short bowel syndrome.
- ✓ 15. No history of clinically significant medical conditions or any other reason that the investigator determines would **interfere with the subject's participation** in this study or would make the subject an unsuitable candidate to receive study drug.
- ✓ 16. No participation in an interventional study within 30 days before Screening (Visit 1) or plans to receive study intervention (other than that administered during this study)
- ✓ 17. No fecal impaction at Visit 2 (Preintervention) after failing outpatient clean-out during the Screening Period OR no fecal impaction at Visit 3 (enrollment/randomization).
- ✓ 18. No required manual dis-impaction within 6 months prior to enrollment/randomization
- ✓ 19. No current condition of unexplained AND clinically significant alarm symptoms (lower gastrointestinal [GI] bleeding [rectal bleeding or heme-positive stool], iron-deficiency anemia, or any unexplained anemia, or weight loss) and systemic signs of infection or colitis, or any neoplastic process
- ✓ 20. No surgery that meets any of the following criteria:
 - a) Surgery to remove a segment of the GI tract at any time before Screening (Visit 1)
 - b) Surgery of the abdomen, pelvis, or retroperitoneal structures during the 6 months before the Screening Visit
 - c) An appendectomy or cholecystectomy during the 60 days before Screening (Visit 1)
 - d) Other major surgery during the 30 days before Screening (Visit 1)
- ✓ 21. No known or suspected mechanical bowel obstruction or pseudo-obstruction
- ✓ 22. No known allergy, allergic reaction, or significant sensitivity to the study intervention or its components and/or other medications in the same drug class
- ✓ 23. No history of:
 - a) Celiac disease, or positive serological test for celiac disease or the condition is suspected but has not been ruled out by endoscopic biopsy
 - b) Cystic fibrosis
 - c) Hypothyroidism that is untreated or treated with thyroid hormone at a dose that has not been stable for at least 3 months prior to Screening (Visit 1)
 - d) Down's syndrome or any other chromosomal disorder
 - e) Active anal fissure (investigator has confirmed an active anal fissure and subject reports known anal fissure symptoms [i.e., streaks of blood on the stool or on diaper or toilet paper and pain/crying with bowel movement within 2 weeks prior to Screening]). (Note: Anal fissures that have resolved at least 2 weeks prior to screening would not be exclusionary). However, if in the investigator's opinion, an anal fissure(s) may be the primary cause of subject's Rome IV FC criteria, the subject would not be eligible to participate in the study.
 - f) Anatomic malformations (e.g., imperforate anus, anal stenosis, anterior displaced anus)

- g) Intestinal nerve or muscle disorders (e.g., Hirschsprung disease, visceral myopathies, visceral neuropathies)
- h) Neuropathic conditions (e.g., spinal cord abnormalities, neurofibromatosis, tethered cord, spinal cord trauma)
- i) Lead toxicity, hypercalcemia
- j) Inflammatory bowel disease
- k) Lactose intolerance that is associated with symptoms which could confound the assessments in this study
- l) History of cancer. (Note: Subjects with a history of cancer are allowed provided that the malignancy has been in a complete remission before enrollment/randomization (Visit 3). A complete remission is defined as the disappearance of all signs of cancer in response to treatment)
- 24. No known active SARS-CoV-2 infection. Per local requirements/recommendations SARS-CoV-2 infection should be ruled out before entering the study. Subjects who do not meet SARS-CoV-2 infection eligibility criteria must be screen failed and may re-screen upon recovery from COVID-19.

Concomitant Medications

- 25. Subject did not use a protocol-specified prohibited medicine before the start of the Preintervention Period (Visit 2) or failed to meet the stable-dose requirements of certain medications
- 26. Subject did not use rescue medication on the calendar day before the enrollment/randomization visit and on the day of the enrollment/randomization visit prior to enrollment/randomization.
- 27. Subject did not participate in an interventional study within 30 days before Screening (Visit 1) or is planning to receive study intervention (other than that administered during this study).
- 28. Subject must not have been treated with **any investigational drug** within 30 days or 5 half-lives of the drug (whichever is longer) prior to Screening (Visit 1) or is currently or planning to enroll in another clinical study or was previously enrolled in this study.

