4 INVESTIGATIONAL PLAN

4.1 Overall Study Design and Plan

M21-862 is a phase 2 study to assess the safety of linaclotide (Part 1) and to evaluate the safety and efficacy of linaclotide in pediatric subjects (Part 2) (6 months to less than 2 years of age). The schematic of the study is shown in [Figure 1](#) and [Figure 2](#). Further details regarding study procedures are located in the Operations Manual.

[figure not shown]
See Section 5 for information regarding eligibility criteria.

Figure 1. Study Schematic

TBD = to be determined in Part 1

Figure 2. Study Visit Schematic for Parts 1 and 2

This study consists of 2 Parts that include 4 cohorts in total. Part 1 has three open label cohorts and Part 2 has a double-blind cohort. Part 1 cohorts will be open label and enrolled sequentially with linaclotide in ascending doses. A linaclotide dose will be chosen for Part 2 based on the overall benefit-risk profile of the open label cohort(s) in Part 1. Part 2 will include a double-blind cohort to assess the efficacy of linaclotide vs placebo. All cohorts will have a study intervention period of 4 weeks.

Up to 30 and at least 18 subjects, 6 months to less than 2 years of age, will be sequentially enrolled into this study: six subjects in each cohort for Cohorts 1-3 and twelve subjects for Part 2. Cohorts 1 to 3 will be open label with linaclotide only. Part 2 will be double blinded, and subjects will be randomized at a 1:1 ratio to linaclotide or placebo.

All cohorts will be of 9 to 12 weeks in duration: 0 to 4-week Screening Period (the minimal of 0 to 4-week period only applies to subjects that need wash out from prohibited medications), a 2 to 3-week Preintervention Period, followed by a 4-week Study Intervention Period, and a 1-week Postintervention Period.

In Part 1, linaclotide will be administered orally QD at the dose of 9 µg, 18 µg, and 36 µg for Cohort 1, Cohort 2 and Cohort 3, respectively. Part 2 will include additional subjects at the dose of linaclotide (either the 9, 18, or 36 µg dose) that exhibited the best benefit-risk profile from Part 1; and subjects receiving matching placebo.

In Cohorts 1-3, at least 5 subjects per cohort will need to complete treatment with an acceptable safety profile assessed by an internal Dose Escalation Review Committee which will give special attention to the presence of AESIs for the cohort to be declared safe to escalate to the next dose level.

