In each cohort of Part 1, at least 1 subject will need to be \leq 12 months of age. The study investigator and the LAR/parent/guardian will be given the option for the subject to continue in the next higher cohort (dose escalation) if the safety profile favors a trial cohort at a higher dose. In Part 1, new subjects will be recruited for each cohort, but existing subjects from previous cohorts (Cohorts 1 and 2) will be given the opportunity to participate in the next cohort (up to Cohort 3) if their symptoms have not improved at that respective dose (\leq 2 SBM per week), the subject has an acceptable tolerability to the study drug, and the LAR/parent/guardian is willing to continue in the study.

Subjects who are participating in intrasubject dose escalation will need to repeat all screening procedures and eDiaries if $>$ 30 days have elapsed since the subject's last dose in the previous cohort. Note: the screening number assigned by the Interactive response technology (IRT) at the initial screening visit should still be used. If symptoms have improved at the current dose level, the subject will be invited to participate in a long-term safety extension study, once the study is active and accepting subjects. An internal Dose Escalation Review Committee will be monitoring the safety of Cohorts 1-3 and will provide a recommendation for the dose escalation to the next cohort or to stop the study based on the overall benefit-risk profile. The dose will be selected based on: 1) the absence of treatment-related AESI within the cohort and 2) an increase in SBM frequency per week compared to baseline with or without improvement of at least 1 point in the Bristol Stool Form Scale (BSFS) scale. The minimum effective dose will be selected.

Once the best benefit-risk dosing profile from Cohorts 1-3 has been identified, Part 2 (the final cohort) will include 12 subjects at 4 weeks of double-blind study intervention with linaclotide vs. placebo using that selected dose. An independent DSMB will review unblinded interim safety data for that cohort. Based on this review, the DSMB will assess the overall safety of the subjects in Part 2.

In Part 2, new subjects will be recruited. Data based on the final selected dose will be analyzed and compared with a placebo. Similarly, safety and efficacy will be analyzed across all cohorts (Parts 1 and 2) and to placebo. Those results will be used to support the feasibility of a confirmatory Phase 3 study.

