5.11 Data Safety Monitoring

Part 1 Open Label Cohorts

In Part 1 all AE data and the occurrence of intolerable diarrhea will be reported to the sponsor. The Internal Dose Escalation Review committee will monitor Part 1 and based on the frequency and severity of the events, could recommend halting the administration of the investigational product (more details are described in a separate charter). The Internal Dose Escalation Review committee will also give special attention to the presence of AESIs. A cohort will be stopped if 1 treatment-related AESI occurs. If no treatment-related AESI occurred, the Dose Escalation Review Committee will decide on whether to proceed with the next cohort.

Part 2 Randomized Double Blind Placebo Controlled Cohort

In Part 2 an external DSMB composed of clinicians and statisticians independent of AbbVie and with relevant expertise in their field will review unblinded safety data from the ongoing study. The DSMB is responsible for safeguarding the interests of trial subjects, assessing the safety of the interventions during the trial, as well as for monitoring the integrity and interpretability of the trial. The DSMB will provide recommendations to the sponsor regarding ongoing trial conduct or modifications to the trial as described in a separate DSMB charter.

In order to maintain sponsor blinding, an external Statistical Data Analysis Center is responsible for performing the analyses described in the DSMB charter as well as additional analyses requested by the DSMB and facilitating interpretation and answering questions that arise before, during or after DSMB review. An independent DSMB will review unblinded interim safety data for Part 2.

The DSMB will regularly review unblinded safety data from the ongoing study according to the schedule provided in the DSMB charter, including AEs, laboratory values, vitals sign values and ECG results. The occurrence of intolerable diarrhea will be reported to the sponsor and will be monitored; In addition to all AE data, by an external DSMB, who, based on the frequency and severity of the events, could recommend halting the administration of the investigational product.

A separate DSMB charter will be prepared outside of the protocol and will further describe the roles and responsibilities of the DSMB members, frequency and scope of the data reviews, and expectations for blinded communications.

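### The per-kg case for 36 µg assumes a minimum weight of 5 kg, but no check before the first 36 µg dose enforces it (low-cost tightening; 9 and 18 µg are not affected)

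*Protocol*

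**What the plan says.** Protocol Section 4.2 (Dose Justification) converts the fixed doses to µg/kg at an assumed 5 kg, described as "minimum weight of a 6 month old), respectively and are therefore equivalent to the doses tested and safe in 2- to 5- year-old subjects" on a per-kg basis. The comparator is LIN-MD-67, in which 18, 36 and 72 µg are converted at an assumed 10 kg for a 2-year-old.

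Dosing goes by cohort, not weight. Section 4.1 states "In Part 1, linaclotide will be administered orally QD at the dose of" 9, 18 and 36 µg for Cohorts 1, 2 and 3, and Part 2 uses one of these doses. Planned numbers are "six subjects in each cohort for Cohorts 1-3 and twelve subjects for Part 2", with Part 2 randomized 1:1.

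On body size, Section 5.1 has criterion 6: "Subject has weight-for-height/length ratio of" at least the 3rd percentile, at the time of consent. Criterion 4 sets age at consent. No criterion gives a value in kilograms, a weight-for-age limit or a gestational-age limit.

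Children can also reach 36 µg by escalation: "existing subjects from previous cohorts (Cohorts 1 and 2) will be given the opportunity to participate in the next cohort (up to Cohort 3"), subject to non-improvement, tolerability and willingness. On rescreening, Section 4.1 says "Subjects who are participating in intrasubject dose escalation will need to repeat all screening procedures and eDiaries if" more than 30 days have passed since the last dose in the previous cohort.

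**The concern.** The per-kg equivalence holds for a child on 36 µg only if that child weighs at least 5 kg. The protocol states that weight as a premise and never turns it into a condition. Weight-for-length does not do so, because a child who is both short and light can sit above the 3rd percentile.

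Escalating children add a second route. A child who entered at 9 or 18 µg and moves up within 30 days need not repeat screening, so a weight condition checked only at Screening would not reach that child.

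At stake is whether a few of the smallest infants could receive a per-kg dose above the value the sponsor uses to describe 36 µg as already tested. Operations Manual Section 3.8 leaves open whether systemic exposure is higher in this age group than in older children and adults, and the pharmacokinetic sampling meant to address this is optional.

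**Working it through.** **Inputs.** All are from the protocol: doses of 9, 18 and 36 µg and the assumed 5 kg (Section 4.2); LIN-MD-67 doses of 18, 36 and 72 µg and the assumed 10 kg (Section 4.2); cohort sizes and the 1:1 ratio (Section 4.1). Weights below 5 kg are assumptions for illustration. The documents give no weight distribution for this study and no actual weights for LIN-MD-67.

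**1. Reproduce the plan's figures** (dose ÷ weight).
- This study at 5 kg: 9/5 = 1.8; 18/5 = 3.6; 36/5 = 7.2 µg/kg.
- LIN-MD-67 at 10 kg: 18/10 = 1.8; 36/10 = 3.6; 72/10 = 7.2 µg/kg.

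The stated values reproduce exactly.

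**2. Weight at which each dose reaches 7.2 µg/kg** (dose ÷ 7.2).
- 9 µg: 1.25 kg
- 18 µg: 2.5 kg
- 36 µg: 5.0 kg

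**3. Dose per kg below 5 kg.**

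| Assumed weight | 9 µg | 18 µg | 36 µg | 36 µg relative to 7.2 |
|---|---|---|---|---|
| 4.9 kg | 1.84 | 3.67 | 7.35 | +2.0% |
| 4.8 kg | 1.88 | 3.75 | 7.5 | +4.2% |
| 4.5 kg | 2.0 | 4.0 | 8.0 | +11.1% |
| 4.0 kg | 2.25 | 4.5 | 9.0 | +25.0% |

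Below 5 kg, 9 and 18 µg also rise above their own paired values (1.8 and 3.6) but stay well inside the range up to 7.2. Only 36 µg leaves it.

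**4. Children planned to receive 36 µg.**
- 0 if Cohort 3 does not open.
- 6 if only Cohort 3 uses it.
- 6 + 12 × 1/2 = 12 of 30 (40%) if Part 2 also uses it.

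Any escalating children counted on top of the six would add to this. These are children given 36 µg, not children under 5 kg; the latter number cannot be derived from the documents.

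**5. Does any existing rule enforce 5 kg?**
- Criterion 4: age only.
- Criterion 6: relative to length, at consent.
- Criteria 5 and 15: investigator judgement, no weight named.
- Criterion 19: unexplained weight loss, not low weight.
- Criterion 23: named conditions, some of which go with small size.
- Escalation rules: no weight condition.
- Visit 3: weight is measured (Operations Manual Section 2.1), but no threshold or action is attached.

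None does.

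**The case against.** The strongest reply is that this concerns a child the documents do not show. The protocol itself calls 5 kg the minimum at 6 months. Age is fixed at consent and at least 2 weeks of Preintervention follow, so every child is older than 6 months at first dose, and escalating children are older again by a treatment period. The protocol counts weight among the vital signs, so criterion 5 lets an investigator exclude a worryingly light infant, and criteria 6, 15, 19 and 23 narrow the group further. All of this stands, and it makes the case rare. It still leaves the limit to discretion.

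Second, 7.2 µg/kg is not a safety boundary. It is a nominal match with an assumed weight on each side, and Section 4.2 also draws on Phase 2 data from ages 2 to 17, adult Phase 3 data and flat GC-C expression from 6 months. Absorption in adults is minimal. This stands, and it is why the excesses above should not be read as measures of harm.

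Third, protection is sequential. At least five children must complete each lower dose with acceptable safety, "A cohort will be stopped if 1 treatment-related AESI occurs", and for Part 2 "The minimum effective dose will be selected". These are real safeguards, but the stopping rule acts after an event, and clean results at 9 and 18 µg do not bring 36 µg within 7.2 µg/kg for a child under 5 kg.

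Fourth, infants usually gain weight, so an earlier weight would normally be the lower one. That is fair for a child screened directly for Cohort 3. A child who entered at 9 or 18 µg, where no floor is needed, would never have been tested against one.

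**Conclusion.** The concern holds, as an optional, low-cost tightening. The arithmetic in Section 4.2 is correct; its 5 kg premise is not enforced for the one dose that depends on it. The excess would be 2% at 4.9 kg and 25% at 4.0 kg, and it could arise only among the 0 to about 12 planned recipients of 36 µg, plus any additional escalating children.

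This rests on two assumptions: that an otherwise eligible infant under 5 kg can occur, which the documents neither show nor exclude, and that the sponsor intends the per-kg match to apply to every child starting 36 µg. No claim is made that 36 µg is unsafe below 5 kg, and the point does not bear on the descriptive analyses.

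**What to change.** Add one condition for 36 µg only: *Body weight of at least 5 kg at Visit 3, confirmed before enrollment/randomization and before the first 36 µg dose.*

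- Apply it to Cohort 3, including children escalating from Cohorts 1 or 2 whether or not they repeat screening.
- Apply it to Part 2 if 36 µg is selected. Checking before randomization keeps the two arms alike.
- Set no floor for 9 or 18 µg, and change no dose.

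The cost is one line of text and no new procedure, since weight and eligibility are already on the Visit 3 list. As a protocol change it needs IEC/IRB approval (Section 8.1), so it is best carried in the next amendment. A very small number of light infants could not receive 36 µg, or could not enter Part 2 at that dose, and Cohort 3 would have a slightly different entry rule from Cohorts 1 and 2. An infant could also be turned away after the diary period; the weights from Visits 1 and 2 can warn sites early, with the Visit 3 weight deciding.
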